3.5.2 Additional Effectiveness Endpoints

The following endpoints will be descriptively analyzed in LUX-Dx monitored Treatment Subjects with CTI Ablation using the FARAPoint PFA Catheter at the indicated time points:

- **CTI-Mediated AFL Treatment Success**

Defined as both of the following outcomes:

CTI-Mediated AFL Acute Procedural Success: defined as the absence of conduction through the cavo-tricuspid isthmus in both directions achieved with the FARAPoint PFA Catheter, confirmed at the end of the Index Procedure/Rescheduled Index Procedure. Use of a catheter modality for treatment of CTI-

Mediated AFL other than FARAPPOINT PFA Catheter will be considered a CTI-Mediated AFL Acute Procedural Failure.

CTI-Mediated AFL Chronic Success: defined as freedom from documented recurrence of CTI-mediated AFL as of the Day 90, Day 180, and Day 360 Assessment(s), without repeat CTI ablation. If recurrence of AFL is indicated on the LUX-Dx recording, recurrence of CTI-mediated AFL must be confirmed with a 12-lead ECG.

- **Re-ablation Rate for CTI-Mediated AFL**

Defined as the proportion of subjects who receive one or more re-ablations during study follow-up for CTI-Mediated AFL, at any time during follow-up, and subdivided by Day 90 and Day 180 Assessment.

The following endpoints will be descriptively analyzed in all LUX-Dx monitored Treatment Subjects at the indicated time points:

- **Persistent AF Acute Procedural Success**

Defined in **Section 3.4.1** at the conclusion of the Index Procedure / Rescheduled Index Procedure

- **Persistent AF Chronic Success**

Defined in **Section 3.4.2** through the Day 360 assessment

- **Freedom from Detectable AF, AFL, AT**

Defined as freedom from recurrence of any Detectable AF, AFL, or AT as defined in **Section 23.2** and additionally assessed using different minimum thresholds for the duration of asymptomatic episodes which count as recurrence of AF, AFL, or AT based on continuous monitoring after the blanking period. Thresholds will include 30 seconds, 4 minutes, 6 minutes, 1 hour, 6 hours, and 24 hours.

- **Freedom from Symptomatic Recurrence and Intervention to Treat AF, AFL, or AT**

Defined as freedom from recurrence of any symptomatic Detectable AF, AFL, or AT as defined in **Section 23.2** and freedom from intervention to treat AF, AFL, or AT, including re-ablation, cardioversion, or use of a Non-Failed Class I/III AAD or amiodarone.

- **Single Procedure Treatment Success**

Treatment Success as defined in **Section 3.4** but counting subjects with any re-ablation for AF, AFL, or AT as Treatment Failures

- **Off Drug Treatment Success**

Treatment Success as defined in **Section 3.4** but counting subjects treated with any Class I / III AAD after Day 90 as Treatment Failures

- **Re-Ablation Rate**

Defined as the proportion of subjects who receive one or more re-ablations during study follow-up for AF, AFL, or AT, at any time during follow-up, and subdivided by re-ablation during Days 0 – 90 and by Days 91 and thereafter. CTI only re-ablation is excluded for subjects who did not receive CTI ablation with the FARAPPOINT catheter.

- **AF, AFL, and AT Burden**

Descriptive statistics on AF, AFL, and AT burden, as defined in Section 23.2 and assessed during the observation period from Day 91 to Day 360 Assessment. AF, AFL, and AT burden will also be calculated for the days from LUX-Dx activation to the Index/ Rescheduled Index Procedure (up to 30 days pre-procedure) and compared to the burden calculated from Day 91 to Day 360 Assessment. Additionally, AF, AFL, and AT burden statistics from Day 91 to Day 360

will be stratified by recurrence based on LUX-Dx detected AF, AFL, or AT using various episode duration thresholds.

- **Healthcare Utilization by AF, AFL, and AT Burden**

Healthcare utilization, defined by outcomes of all-cause hospitalization, cardioversion for AF, AFL, or AT recurrence outside of an ablation procedure, re-ablation for AF, AFL, or AT and unscheduled cardiovascular follow-up assessments, will be compared between subjects grouped by AF, AFL, and AT burden from Day 91 to Day 360 Assessment. Burden groups will include rates of 0%, 0-0.1%, 0.1-1%, 1-5%, 5-10%, and >10% AF, AFL, and AT burden.

- **Healthcare Utilization by AF, AFL, or AT Recurrence Duration**

Healthcare utilization, defined by outcomes of all-cause hospitalization, cardioversion for AF, AFL, or AT recurrence outside of an ablation procedure, re-ablation for AF, AFL, or AT and unscheduled cardiovascular follow-up assessments will be compared between subjects grouped by longest duration of AF, AFL, or AT captured by LUX-Dx (based on continuous monitoring) between Day 91 and Day 360 Assessment. Groups will include no recurrence and longest duration of 0-6 minutes, 6 minutes – 1 hour, 1-6 hours, 6-24 hours, and \geq 24 hours.

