Although AF and CTI-dependent atrial flutter (AFL) are different arrhythmias with their own mechanisms and electrophysiologic presentation, their interrelationship has long been recognized and they coexist in a significant percentage of patients.⁶ The relationship is reciprocal since patients diagnosed with AFL may develop AF after CTI ablation and patients with AF often go on to develop AFL.⁷⁻⁹ In particular, the presentation of AFL in the context of AF may be the sign of additional atria remodeling or the presence of non-PV triggers.¹⁰

Accordingly, a strategy that includes both Pulmonary Vein Isolation (PVI) and CTI ablation has become an established practice in the percutaneous ablative treatment of patients with AF. The current guidelines for the management of AF indicate that CTI ablation may be beneficial during procedures of AF ablation, in particular for those patients with history of typical AFL and where AFL is induced at the time of AF ablation.¹¹ Adjunctive prophylactic CTI isolation is emerging as a potential strategy during AF ablation as a means to reduce rates of AFL. Previous studies reported that prophylactic CTI ablation may lead to recurrence rates of AFL lower than or equal to those for AF ablation only.¹²⁻¹⁵ Additionally, adjunctive CTI ablation may mitigate the effect of adjunctive non-PV triggers on AF recurrences in patients with Persistent AF (PersAF).¹⁶

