7.7.2.5 CTI Ablation

The following subjects will undergo CTI ablation with the FARAPoint PFA Catheter:

- Required: For subjects with a history of CTI-mediated (typical) AFL and
 - Who have not had a CTI ablation procedure, or
 - Who have had a CTI ablation procedure but have recurrent CTI conduction.
- Required: Subjects who manifest CTI-mediated AFL (spontaneous or induced) during the Index Procedure
- At Investigator discretion: Subject welfare indicates that CTI ablation should be performed.

CTI Ablation with the FARAPoint PFA Catheter will be performed according to the IFU documents and institutional practice. Per the FARAPoint Catheter IFU, no more than two energy applications should be delivered at any given catheter placement. Repeat placement of the FARAPoint Catheter at nearly identical locations should be avoided unless there is a clear clinical need for such placements.

The FARAWAVE Catheter is not allowed to complete any CTI lesion.

CTI ablation with the FARAPoint PFA Catheter must adhere to the following protocol requirements in order to mitigate the risk of coronary spasm during ablation application.

No ablations outside CTI with the FARAPoint PFA Catheter are allowed.

The following prophylactic workflow is required to be followed when CTI ablation is performed with the FARAPoint PFA Catheter:

- **Pre-Treatment (Required)**: Administer a three milligrams (3mg) nitroglycerin IV bolus via the FARADRIVE sheath (or other sheath with central access) approximately one minute prior to the first PFA application at the anterior position of the CTI line.
- **During Ablation (Required)**:

⁷ If anesthesia necessitates, a pre-discharge fluoroscopic sniff test or inspiration / expiration CXR may be acceptable. See **Section 7.8**.

- Depending upon procedure duration and patient condition, administer an additional 2mg IV bolus via the FARADRIVE sheath (or other sheath with central access) approximately two (2) minutes apart until the ablation is complete or a maximum total of 9mg IV of nitroglycerin has been administered.
- If bidirectional block (BDB) is assessed and not present and additional ablation lesions are required in the anterior aspect of the cavo-tricuspid isthmus line, Investigator discretion will determine whether to administer an additional 2-3 mg of nitroglycerin IV via the FARADRIVE sheath (or other sheath with central access) prior to re-ablation.

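### The FARAPOINT CTI endpoints omit attempted cases ablated only with another catheter, and they pool flutter patients with discretionary cases that can lift the chronic result

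*Combined protocol and SAP*

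**What the plan says.** Appendix A, 3.5.2, Additional Effectiveness Endpoints, opens with two CTI endpoints, CTI-mediated AFL treatment success and the re-ablation rate for CTI-mediated AFL. Both "will be descriptively analyzed in LUX-Dx monitored Treatment Subjects with CTI Ablation using the" FARAPOINT catheter.

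Treatment success needs two outcomes:

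- Acute success is "the absence of conduction through the cavo-tricuspid isthmus in both directions achieved with the FARAPoint PFA Catheter", confirmed at the end of the index procedure. Treating CTI-mediated AFL with any other catheter modality "will be considered a CTI-Mediated AFL Acute Procedural Failure".
- Chronic success is "freedom from documented recurrence of CTI-mediated AFL as of the Day 90, Day 180, and Day 360 Assessment(s), without repeat CTI ablation".

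Appendix A, 7.7.2.5, gives three routes to CTI ablation with FARAPOINT. Two are required: a history of typical flutter, or CTI-mediated flutter seen during the procedure. The third needs neither: "At Investigator discretion: Subject welfare indicates that CTI ablation should be performed".

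Appendix A, 4.1.2, expects about 30% of the 258 Treatment Subjects to receive FARAPOINT, allows enrolment to be steered so that an estimated 80 do, and sets no upper limit. Section 8.1.3 makes the additional endpoints descriptive.

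**The concern.** There are two separate problems.

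**Denominator.** The failure rule and the analysis set do not match at one edge. Suppose FARAPOINT is inserted for CTI-mediated flutter, delivers no CTI ablation, and another catheter does the work. The definition calls that an acute failure. The set, read as written, excludes the subject because no CTI ablation was done with FARAPOINT. The omitted cases are those in which the catheter could not do its job, so leaving them out can only raise the reported acute rate, or leave it unchanged if there are none.

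**Mixture.** Freedom from recurrent CTI flutter means one thing in a patient who had that flutter and another in a patient who may never have had it. The set combines them, and no CTI result is planned by indication. Appendix A, 1.1, notes as background that "Adjunctive prophylactic CTI isolation is emerging as a potential strategy during AF ablation", so a discretionary share above zero is plausible.

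Phase 2 seeks approval of FARAPOINT for adjunctive use, and primary acute success (3.4.1) concerns only the pulmonary veins and posterior wall. CTI-mediated AFL treatment success is the one effectiveness measure that combines CTI block with CTI-specific recurrence, so its denominator and mix of patients deserve care even though nothing is tested on it.

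**Working it through.** **Step 1. The plan's own figure.** 0.30 × 258 = 77.4, and 80 / 258 = 31.0%. The stated 80 agrees with an approximate 30%. It is the count before the restriction to LUX-Dx monitored subjects. The endpoint has no sample size, goal, alpha or power to reproduce.

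**Step 2. Who is in the set and how each case is scored.**

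| Index CTI ablation for CTI-mediated AFL | Under the failure rule | In the analysis set? |
|---|---|---|
| FARAPOINT only, block achieved | Success | Yes |
| FARAPOINT only, no block | Failure | Yes |
| FARAPOINT, then another catheter | Failure | Yes |
| FARAPOINT inserted, only another catheter ablates | Failure | **No** |

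The last subject can still be a Treatment Subject. Phase 1 section 6.6.5, which Appendix A adopts, needs one pulsed field application from any study catheter, and FARAWAVE supplies it.

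**Step 3. Is the omitted case recovered elsewhere?** It is not. The Phase 2 definition of Detectable AF, AFL or AT (23.2) leaves out CTI-dependent flutter in subjects without FARAPOINT CTI ablation. The general re-ablation rate in 3.5.2 leaves out their CTI-only re-ablations. The separate summary in 8.2.1 covers only subjects lacking a LUX-Dx device or LATITUDE connection. The CTI subgroup in 8.3.4 compares CTI ablation with none, for the primary endpoints.

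**Step 4. Size of the denominator effect.** Let p be the acute rate in 80 included subjects and k the omitted failures. Counting them gives 80p / (80 + k), a fall of p × k / (80 + k). Both p and k are assumptions.

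| Rate in the 80 | k = 1 | k = 2 | k = 4 | k = 8 |
|---|---|---|---|---|
| 64/80 = 80.0% | 79.0% | 78.0% | 76.2% | 72.7% |
| 72/80 = 90.0% | 88.9% | 87.8% | 85.7% | 81.8% |
| 76/80 = 95.0% | 93.8% | 92.7% | 90.5% | 86.4% |

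The first omitted case is worth p / 81, or 1.0 to 1.2 points for p between 80% and 95%.

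**Step 5. Size of the mixture effect.** Let s be chronic freedom from CTI flutter in required cases, u in discretionary cases, and d the discretionary share. The pooled rate is (1 − d)s + du, which differs from s by d(u − s). It is too high only if u exceeds s. All three are assumptions.

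- *Upper end, u = 100%.* As an anchor only, take s = 82.4%, from the 14 of 17 subjects with durable block at remapping in the feasibility study (Appendix A, 1.2). That is block durability, not flutter recurrence. The pooled rate is 86.8%, 91.2% and 95.6% for d = 25%, 50% and 75%. With s = 80% it is 85%, 90% and 95%; with s = 90% it is 92.5%, 95.0% and 97.5%.
- *Milder case.* Recurrence of 10% in required and 1% in discretionary cases, with d = 40%, gives 0.6 × 10% + 0.4 × 1% = 6.4%, against 10% in the flutter patients.

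The same formula applies to the CTI re-ablation rate. It does not apply to acute success: bidirectional block can be assessed in any subject, whatever the reason for the line.

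**The case against.** **The failure rule already works in the ordinary case.** This stands. A reader might infer that the rule is empty because the set requires FARAPOINT. It is not: a subject ablated with FARAPOINT who then needs RF stays in and is scored a failure. Only cases with no FARAPOINT CTI ablation drop out.

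**Such cases should be rare.** This stands too. Section 7.7.2.5 directs index CTI ablation to FARAPOINT, so an RF-only line would usually be a departure from protocol. Section 7.7.2.6 allows commercial RF for spontaneous treatment-emergent flutter, but 3.5.3 describes the flutter in that category as left-sided, so it is weak evidence of a regular RF route to the CTI. The larger values of k above are illustrations, not forecasts.

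**Discretionary lines belong to the intended use.** The indication in Appendix A, 2.1, is the creation of an ablation line between the inferior vena cava and the tricuspid valve, as an adjunct in persistent AF. A reader might infer that only required cases should be the headline. The indication does not support that, and the overall result should remain. Nor is success automatic in discretionary cases: 1.1 says that AF patients often go on to develop flutter.

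**Not every non-FARAPOINT CTI ablation reflects on the catheter.** Agreed. The failure rule concerns treatment of CTI-mediated AFL. A line drawn without any FARAPOINT attempt may reflect a deviation or unavailable equipment, and the documents do not support scoring it as a device failure.

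**The SAP may settle it.** The protocol defers several analysis details to the SAP, and the Phase 2 SAP text was not available for this check. A set definition or listing there cannot be excluded.

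**Conclusion.** The point holds in a limited form. As written, the CTI analysis set leaves out subjects in whom FARAPOINT was attempted for CTI-mediated AFL but only another catheter delivered the ablation, although the definition calls them acute failures. The effect is upward, at roughly 1 percentage point per omitted case out of about 80, with few such cases expected. Pooling discretionary with required cases can raise chronic success, and treatment success through it, and can lower the CTI re-ablation rate. This assumes that flutter is less frequent afterwards in the discretionary cases. Acute block is unaffected.

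The actual size cannot be derived, because neither the number of omitted cases nor the discretionary share is given.

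A reader might infer that the trial's conclusion is at risk. It is not. The endpoints are additional and descriptive, and study success rests on the two primary endpoints (8.2.3), so type I error and the sample size of 258 are unaffected. In FARAPOINT-treated subjects, CTI flutter also counts against the primary effectiveness endpoint (23.2). What suffers is the reading of the CTI-specific evidence for the added catheter, which is reason enough for an inexpensive correction.

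**What to change.** In Appendix A, 3.5.2, and the SAP:

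1. Define the set for the CTI endpoints as LUX-Dx monitored Treatment Subjects in whom CTI ablation with FARAPOINT was attempted, meaning that the catheter was inserted for that purpose.
2. Within it, score subjects whose ablation for CTI-mediated AFL was completed with another catheter as acute failures. They are then treatment failures too, since treatment success needs both parts.
3. List separately, with the reason, any index CTI ablation done without a FARAPOINT attempt.
4. Report acute success, chronic success, treatment success and CTI re-ablation overall and separately for required cases (history or manifest CTI-mediated AFL) and discretionary cases. Read the chronic flutter result from the required group.

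No change to patient care is needed. The rate may be less favourable and the strata are smaller. If half of 80 subjects were required cases, 33 of 40 free of flutter would carry an exact 95% interval of 67.2% to 92.7%, against 72.4% to 90.1% for 66 of 80.

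The sponsor must also confirm that the reason for CTI ablation is recorded or can be derived. Section 7.5 collects cardiovascular history and 7.7.2.5 sends CTI ablation data to the CRF, but 7.7.1 does not list the reason as an item.

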13. Contraindication to ICM insertion	Patients who cannot tolerate a subcutaneous, chronically-inserted LUX-Dx device
14. LUX-Dx longevity	Patients with a LUX-Dx device inserted > 6 months prior to enrollment or an estimated longevity of less than 1 year

6 Subject Enrollment and Accountability

The subject enrollment and accountability sections of Phase 2 of the ADVANTAGE AF study remain the same as Phase 1 and can be referenced in **Section 6** of the Phase 1 clinical investigational plan.

As the LUX-Dx device is not considered an investigational device, if a subject enrolled in the study receives a LUX-Dx device and then withdraws from the study prior to having the FARAPULSE investigational devices inserted into the body, the subject will be classified as an Intent or Consent Ineligible subject (Refer to Phase 1 protocol **Section 6.6.3**).

⁴ Clinical resolution of COVID-19 disease is to be determined by the investigator, based on signs and symptoms of current active viral infection, not long-term sequelae of the disease such as anosmia or chronic fatigue.

7 Study Methods

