7.1 Overview of Study Interactions

Each Treatment subject will undergo the following formal study interactions:

- Baseline Assessment
- LUX-Dx Insertion (Enrollment to Day 7 post Index Procedure, highly recommended to occur 30 days prior to Index Procedure)
- Index Procedure / Rescheduled Index Procedure (Day 0)
- Pre-Discharge Assessment (immediately prior to discharge after the Index Procedure)
- Day 7 Safety Assessment (window Day 7 – 11, remote)
- Day 30 Safety Assessment (window Day 30-37, remote)
- Day 90 Assessment (window 90 ± 14 days, in-person)
- Day 180 Assessment (window 180 ± 30 days, remote)
- Day 360 Assessment (window 360 ± 30 days, in-person)

In addition, the following events may also occur for some study subjects:

- Re-ablation Procedure: Re-ablations for AF, AFL and AT will be captured in the EDC database using the Re-Ablation Procedure CRF
- Unscheduled Assessments: Any unscheduled cardiovascular assessments will be captured in the EDC database using the Unscheduled Assessment CRF.

The data collection schedule for these various interactions is shown in **Table 7.2-1**.

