¹ Baseline Assessments must be generated in the window beginning 30 days (within 180 days for TTE and cardiac CT / MRI) prior to the Consent Date and ending on the date of the Index Procedure.² Assessments that are defined as remote may also be performed at the investigational site (non-remote) at Investigator discretion and subject agreement.³ Baseline assessments include the inclusion / exclusion criteria and the data stipulated in Section 7.5.⁴ Laboratory tests include hematocrit, hemoglobin, electrolytes, blood urea nitrogen, creatinine and if applicable a pregnancy test at baseline, or for the Index or Re-ablation procedure (if baseline pregnancy test done more than 30 days prior to Index Procedure/re-scheduled procedure)⁵ Within 180 days of Consent Date. Must include baseline ventricular wall motion.⁶ MRI / CT cardiac imaging at baseline within 180 days of Consent Date; subsequently only if required if there is a clinical suspicion of PV stenosis⁷ Performed within 48 hours prior to (TEE or CT) or at the procedure prior to transeptal puncture (TEE or ICE).⁸ Only if resolution of phrenic nerve palsy has not yet been demonstrated.⁹ If NIHSS score has increased by 1 or more points or if there is a clinical suspicion of stroke / TIA, then a consulting neurologist will perform a stroke assessment and include the results of a concurrent brain DW-MRI scan.¹⁰ Re-ablation post-Blanking Period procedure data collection will only include adverse events, gaps identified and ablated and number of applications required¹¹ Required post-ablation for FARAPoint subjects with ischemic changes on their post-ablation 12-lead ECG only¹² Including one pre- and one post-ablation. If the post-ablation 12-lead ECG indicates any changes, an additional 12-lead ECG is required prior to hospital discharge.¹³ Required insertion between enrollment and up to 7 days after the Index/Rescheduled Index Procedure; highly recommended to occur 30 days prior to Index Procedure

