A LUX-Dx is required for post ablation rhythm monitoring for all Roll-In and Treatment Subjects. As described in the **Section 5**, subjects with an active LUX-Dx inserted within 6 months of enrollment or an estimated one year or greater of battery life may be considered for participation in ADVANTAGE AF Phase 2. For those subjects enrolled without a pre-existing LUX-Dx ICM, the LUX-Dx insertion must occur after enrollment and within seven (7) days post Index Procedure/Rescheduled Index Procedure. It is highly recommended for the LUX-Dx to be inserted 30 days prior to the Index Procedure to allow collection of baseline arrhythmia assessment. The LUX-Dx insertion shall be performed according to the recommended insertion technique described in the LUX-Dx ICM User's Manual. The study site will collect data associated with the procedure, including printing the LATITUDE Clarity programming report. Subjects enrolled with an active LUX-Dx implanted prior to enrollment in the study must have LUX-Dx programming settings updated, if necessary, in accordance with the initial programming described directly below, and a LATITUDE Clarity programming report printed to document the ICM settings. Enrollment in LATITUDE Clarity can be performed prior to, during, or immediately after the insertion procedure. Subjects should be shown how to use their myLUX patient application to complete manual transmissions when experiencing symptoms, and reminded of the importance to remain connected to the LATITUDE Clarity system throughout the duration of the trial. Subjects who become disconnected from the LATITUDE Clarity system for greater than 7 days should be contacted and notified to reconnect and remain connected through their MyLUX Mobile Patient Device/App.

Initial programming of the LUX-Dx device aligns with all detection algorithm nominal parameters as defined in Table 7.6-1 for Post AF Ablation as the reason for monitoring⁶, in addition to those parameters listed in **Table 7.6-1** below.

⁶The LATITUDE Clarity Alert Settings are associated with the Post AF Ablation reason for management settings with exception of turning on the Alert for AT Events – which is not a nominal setting for “Post AF Ablation” reason for monitoring).

Table 7.6-1: LUX-Dx Initial Parameter Settings

Parameter	Post AF Ablation Setting	Latitude Clarity Alert Setting
AF Detection	On	Alert for AF Event – On
AF Response	More	Yellow Alert
AF Duration	4 min	
Pause Response	Less	Alert for AF Event – On

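### The pre/post burden comparison starts its baseline at LUX-Dx activation rather than at study programming, and does not say it is made within subjects

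*Combined protocol and SAP*

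**What the plan says.** Appendix A section 3.5.2 lists burden among the additional effectiveness endpoints, analysed descriptively in all LUX-Dx monitored Treatment Subjects. The main statistic covers Day 91 to the Day 360 Assessment. A pre-procedure figure is added: "AF, AFL, and AT burden will also be calculated for the days from LUX-Dx activation to the Index/ Rescheduled Index Procedure". The same sentence then sets the cap and the comparison: "up to 30 days pre-procedure) and compared to the burden calculated from Day 91 to Day 360 Assessment".

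Three other provisions decide what those baseline days contain.

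- **Pre-existing devices are admitted.** Section 5.3 excludes only this group: "Patients with a LUX-Dx device inserted > 6 months prior to enrollment or an estimated longevity of less than 1 year".
- **Their settings are changed later.** Section 7.6 says: "Subjects enrolled with an active LUX-Dx implanted prior to enrollment in the study must have LUX-Dx programming settings updated, if necessary". It gives no date for the update relative to consent or the procedure, but does require a LATITUDE Clarity programming report to document the settings.
- **New devices may come late.** For subjects without one, section 7.6 says "the LUX-Dx insertion must occur after enrollment and within seven (7) days post Index Procedure/Rescheduled Index Procedure". The schedule in section 7.2 repeats this in footnote 13: "Required insertion between enrollment and up to 7 days after the Index/Rescheduled Index Procedure". Insertion 30 days before the procedure is strongly recommended but not required.

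Appendix A section 23.2 defines burden as the duration of device-detected AF and AT episodes adjudicated as true, divided by follow-up time less the duration of episodes with no stored ECG.

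**The concern.** Burden is built from what the device detects, and detection depends on how the device is programmed. Table 7.6-1 sets an AF duration of 4 minutes and an AT duration of 4 hours at 110 bpm. Section 2.3.1 says default detection parameters follow the reason for monitoring, and the study settings are those for monitoring after AF ablation. A device inserted before enrollment may well have been set up for another reason. The sponsor recognises the general problem in section 8.1.2, where it names differences in ICM programming and in insertion timing relative to ablation when explaining why published ICM results cannot be combined.

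Two things follow. A change in measured burden within a subject could partly reflect a change of settings inside the baseline. A change in the group figure could partly reflect different subjects supplying the two periods. This is the only pre/post rhythm comparison in section 3.5.2, section 1.4 states an aim of helping to define a burden standard for future persistent AF studies, and none of the sensitivity analyses in section 8.3.3 covers it.

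**Working it through.** The plan states no sample size, power or effect size for this comparison, so there is no figure to reproduce. The check is on the two windows.

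**Post-ablation window.** Day 91 to the Day 360 Assessment, with section 7.1 giving "Day 360 Assessment (window 360 ± 30 days, in-person".

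- Earliest: 330 − 91 + 1 = 240 days
- Nominal: 360 − 91 + 1 = 270 days
- Latest: 390 − 91 + 1 = 300 days

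**Baseline window.** 0 to 30 days, because of the cap.

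**Share of the baseline under earlier settings.** Take a pre-existing device, active at least 30 days before the procedure, whose settings differed from Table 7.6-1. Let g be the days from consent to the procedure and r the days from consent to reprogramming. The Phase 1 protocol, section 6.1.3 (carried over by Appendix A section 6), bars study-specific procedures before consent and requires the Index Procedure within 30 days of it; a rescheduled procedure can add up to 45 days. Then

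share s = max(0, 30 − (g − r)) / 30

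| g (days) | r = 0 | r = 7 |
|---|---|---|
| 7 | 23/30 = 77% | 30/30 = 100% |
| 14 | 16/30 = 53% | 23/30 = 77% |
| 21 | 9/30 = 30% | 16/30 = 53% |
| 30 | 0% | 7/30 = 23% |

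Unless the procedure is rescheduled, such a subject has a full 30-day baseline free of earlier settings only if reprogrammed on the consent day and ablated on day 30.

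**Effect on one subject's baseline.** If B_old and B_study are the burdens that the two settings would show, and analysable time is similar across the days, the recorded baseline is s × B_old + (1 − s) × B_study. The error is s × (B_old − B_study). The documents give s a range, as above, but say nothing about B_old − B_study.

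**Effect of different subjects.** Let f be the fraction of monitored subjects with any baseline, B_w and P_w their mean pre and post burden, and P_o the mean post burden of those without a baseline. Comparing everyone's post burden with the available baselines gives

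f × P_w + (1 − f) × P_o − B_w = (P_w − B_w) + (1 − f) × (P_o − P_w)

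The first term is the within-subject change; the second is not an ablation effect. It vanishes only if f = 1 or the two groups have equal post burden. Neither f nor the two means is given.

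**Coarseness of short baselines.** One minimum-length 4-hour AT episode is 4/24 = 16.7% burden over 1 day, 4/168 = 2.4% over 7 days, 4/720 = 0.56% over 30 days and 4/6,480 = 0.06% over 270 days.

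**The case against.** The strongest reply is that this is a supplementary figure on a descriptive endpoint. It has no hypothesis, no alpha and no part in study success, and section 3.5.2 puts the Day 91 to Day 360 statistic first. That stands, and it limits how much the point can weigh.

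Several stronger readings are tempting and should not be drawn.

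- **Six months of earlier data enter the baseline.** They do not: the 30-day cap follows directly in the same sentence.
- **Every baseline mixes settings.** Only pre-existing devices whose settings differed are affected, since the update is made only where needed.
- **The plan pools subjects without a baseline.** It does not say so. Such a subject has no pre-procedure burden to calculate; the gap is that pairing is unstated. A Phase 2 SAP is referred to for further detail and might specify it, but section 23.2 defers only episode adjudication.
- **30 against about 270 days is biased by length.** Burden is a ratio, so unequal length adds noise rather than bias. Nor must a one-day baseline sit near 0% or 100%, as the 16.7% example shows.

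It is also fair to say that subjects enter with documented continuous AF, and sustained AF leaves limited room for a 4-minute threshold to change measured burden. That argues for a small B_old − B_study in many subjects. It would not cover a subject cardioverted before the procedure or a device with AF detection switched off.

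Finally, the post period is not a clean reference. Sections 7.10 to 7.13 and 7.15 allow the ICM to be reprogrammed after a confirmed recurrence, so a repair to the baseline alone would not put all days under the same settings.

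**Conclusion.** The point holds in a limited form. Following section 3.5.2 as written can put days recorded under non-study settings into the baseline of subjects who enrol with a differently programmed LUX-Dx. Read literally, it also compares those who have a baseline with all monitored Treatment Subjects. For an affected subject the share of baseline days concerned ranges from 0% to 100%, and is 77%, 53% or 30% for reprogramming at consent 7, 14 or 21 days before the procedure.

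These are shares of days, not a measured bias in burden. They assume a device active for the full 30 days and settings that really differed. The number of affected subjects, the number without a baseline, and the direction and size of any effect on burden cannot be obtained from the documents. The comparison should be corrected before analysis because the repair is simple; the study's primary conclusions do not depend on it.

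**What to change.** Amend Appendix A section 3.5.2, and the SAP to match:

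1. Start the baseline at the latest of 30 days before the Index or Rescheduled Index Procedure, LUX-Dx activation, and the date on which Table 7.6-1 settings were confirmed on the programming report that section 7.6 already requires.
2. State that the comparison is made within subjects who have both a baseline and Day 91 to Day 360 data.
3. Report the number of such subjects and their median baseline days, so that readers can judge how coarse the baselines are.
4. Give Day 91 to Day 360 burden separately for subjects without a baseline.
5. Flag subjects whose ICM was reprogrammed after a confirmed recurrence, because their post period of 240 to 300 days is not wholly under study settings either.

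A minimum baseline length is the sponsor's choice; the documents offer no basis for a particular number of days.

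The cost is fewer subjects and fewer baseline days in the comparison. No new assessment is needed. Table 7.18-1 keeps insertion data at the center, so the sponsor should check that the date of confirmed settings can be retrieved for analysis.
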